# 9.2.13 Interactive Response Technology

The IRT will be used to assign patients to treatment arms, manage IMP supply, and to provide treatment allocation information in the event of patient unblinding.

A member of the trial team must contact the IRT at each clinic visit in order to perform the following:

- Randomize a patient (Visit 2)
- Obtain IMP dispensing information (Visits 2, 3, 4, and 5)
- Provide completion/premature termination information (Visit 6)

Training will be given to all sites prior to the start of the trial.

# SPONSOR: GW PHARMA LIMITED

# 9.2.14 Electronic Patient Diary

As part of the baseline period, patients will record their spasm count, 11-point NRS spasm severity score, 11-point NRS spasticity score, and use of antispasticity medications in the electronic diary once daily, around the same time each day, during the baseline period prior to Visit 2 and throughout the trial until Visit 7, unless otherwise indicated. Patients are expected to start completing their electronic diary in the evening of their screening visit (first day of the 28-day baseline period).

In addition, on the day before PK blood sampling, patients will be prompted to record whether they started their morning and evening doses of IMP within 30 minutes of a meal.

# 9.2.14.1 Electronic Diary Training

Patients will be trained by the site staff on the use of the electronic diary at Screening (Visit 1) and will be instructed on how to record their spasm count, 11-point NRS spasm severity score, 11-point NRS spasticity score, and use of antispasticity medications once daily, around the same time of day, preferably in the evening before retiring to sleep, during the baseline period prior to Visit 2 and throughout the trial until Visit 7. Following randomization during Visit 2, patients will be instructed to log their daily IMP dosing in the electronic diary throughout the treatment period until Visit 6.

# 9.2.14.2 Spasm Severity Numerical Rating Scale

The 11-point NRS is considered a valid and reliable method to assess overall spasticity in patients with MS. It is the standardized patient-related outcome that best identifies a clinically important difference and a minimum clinically important difference.

Patients will be asked to make a daily assessment, at bedtime, to read the question, and to tick the most appropriate number to indicate the severity of his or her spasms over the last 24 hours. The patients will be given a definition of spasm and the question will be phrased as follows:

On a scale of 0 to 10, how severe were your spasms on average over the last 24 hours? Considering 0 as "No spasms" and 10 as "Worst possible spasms".

This information will be recorded in the patient electronic diary.

# 9.2.14.3 Spasticity Numerical Rating Scale

Patients will be asked to make a daily assessment, at bedtime, to read the instruction, and to tick the most appropriate number to indicate the severity of his or her spasticity over the last 24 hours. The patients will be given a definition of spasticity and the question will be phrased as follows:

On a scale of 0 to 10, please indicate your level of spasticity over the last 24 hours, considering 0 as "No spasticity" and 10 as "Worst possible spasticity."

This information will be recorded in the patient electronic diary.

# 9.2.14.4 Use of Antispasticity Medications and Investigational Medicinal Product Dosing Record

Patients will be instructed to record their use of antispasticity medications, including their use of baclofen, tizanidine or dantrolene as part of their optimized oral antispasticity therapy, and their IMP dosing daily in their electronic diary.

# 9.2.15 Questionnaires and Assessments Completed at Scheduled Visits

Questionnaires should be completed by the patient, unless otherwise specified. The same person should administer/complete the questionnaires/assessments in order to maintain consistency, unless otherwise stated. The C-SSRS and T25FW will be administered by a trained assessor.

# 9.2.15.1 Multiple Sclerosis Spasticity Scale

The MSSS-88 is a patient self-report measure of the impact of spasticity (muscle stiffness and spasms) in MS. This 88-item scale captures the patient experience and impact of spasticity, including muscle stiffness, pain and discomfort, muscle spasms, effect on daily activities, ability to walk, body movement, patient feelings, and social functioning. Responses to individual questions can range from "not at all bothered" to "extremely bothered."

# 9.2.15.2 Columbia-Suicide Severity Rating Scale

The definitions of behavioral suicidal events used in this scale are based on those used in the Columbia Suicide History Form. Questions are asked on suicidal behavior, suicidal ideation, and intensity of ideation. At Screening (Visit 1), questions will be in relation to lifetime experiences (baseline). Questioning at all subsequent visits will be in relation to the last assessment (since last visit).

The C-SSRS is to be administered by the investigator or his/her qualified designee at Visits 1 through 6 as indicated in the schedule of assessments (see APPENDIX 1); "qualified designee" is defined as anyone who has completed the C-SSRS training within the past 2 years or has continually administered C-SSRS assessments throughout the trial since obtaining the training certificate. The survey should be completed by the same assessor, where possible, throughout the trial. Assessments will be conducted only if patients are capable of understanding and answering the questions, in the investigator's opinion.

#### SPONSOR: GW PHARMA LIMITED

# 9.2.15.3 Timed 25-Foot Walk

The T25FW is a quantitative measure of lower extremity function and should be performed by a trained assessor. The same assessor should administer the T25FW test throughout the trial where possible. If ambulatory, the patient will be instructed to begin at one end of a clearly marked 25-foot course. They will be instructed to walk the 25 feet as quickly as possible, but safely, and to not slow down until after they have passed the finish line. The task will be immediately administered a second time following the first trial by having the patient walk back the same distance.

Patients will be permitted to use their customary, nonmotorized assistive device (AD) (cane, walking sticks, walker, and rollator) during the T25FW test. The same AD must be used at each assessment and its use documented in the patient record.

# 9.2.15.4 Medication Use Survey

This form consists of 18 questions regarding the use of the IMP. The trained investigator or trial coordinator will complete this survey as an interview with the patient at the End of Treatment Visit or Withdrawal Visit (Visit 6).

The MUS will be completed for all patients in the trial and not only those who have reported a triggering AE or drug accountability discrepancy, although only those with triggering AEs/drug accountability events will be adjudicated for abuse potential (see Section 9.2.18).

# 9.2.15.5 36-Item Short Form Health Survey

The SF-36 is a generic multipurpose, short-form QoL health survey comprising 36 questions self-reported by the patient. It yields an 8-scale profile of functional health and well-being scores as well as psychometrically based physical and mental health summary measures and a preference-based health utility index.

The SF-36 differentiates between physical and mental health and consists of 8 different dimensions (physical functioning, vitality, bodily pain, general health perceptions, physical role functioning, emotional role functioning, social role functioning, and mental health) and is validated for bodily pain and physical function.

The SF-36 scores for each dimension can range between 0 and 100, where higher scores indicate better functional health and well-being.

# 9.2.16 Investigational Medicinal Product Accountability

Records of IMP accountability will be maintained according to Section 5.3.4.

# 9.2.17 Adverse Events

Refer to Section 12 for definitions, procedures, and further information on AE reporting.

Refer to Section 9.2.18.1.1 for the list of triggering AEs of interest associated with monitoring of drug abuse liability.

# 9.2.18 Monitoring of Drug Abuse Liability

There are 2 triggers that will require the investigator or trial coordinator to discuss abuse potential signals with the patient. These are either AEs of interest that may be reported by the patient or drug accountability issues regarding overuse of the IMP or missing vials. Different questionnaires will be completed by the trial site depending upon which trigger occurs (see Figure 9.2.18-1). Irrespective of the above, all patients will be interviewed at the End of Treatment Visit or Withdrawal Visit (Visit 6) and a MUS will be completed by the investigator or trial coordinator (see Section 9.2.15.4). Investigators and trial coordinators will be provided with training on how to complete and perform the processes outlined in this section. This training must be completed and documented by the relevant site staff prior to implementation at the trial site.

#### SPONSOR: GW PHARMA LIMITED

# Figure 9.2.18-1Flow Diagram for Identifying and Evaluating Clinical Trial
Adverse Event Data through Systematic Categorization,
Tabulation, and Analysis which can Illuminate an Abuse
Potential Signal

#### SPONSOR: GW PHARMA LIMITED

# 9.2.18.1 Monitoring of Adverse Events (Abuse Liability)

AE information will be collected according to Section 12.6.

# 9.2.18.1.1 List of Triggering Adverse Events of Interest (Abuse Liability)

During the collection of AEs, if the patient reports an AE consistent with any of the following categories, then the investigator or trial coordinator is required to complete a Supplemental Adverse Event Form (see Section 9.2.18.1.2) and a Site Classification Form (investigator only; see Section 9.2.18.3) following further discussion of the event(s) with the patient. The categories are:

- Addiction
- Disturbance in cognition, memory, or attention
- Drug abuse
- Drug withdrawal or drug withdrawal syndrome
- Drunk, high or intoxicated
- Euphoria or inappropriate elation
- Hallucinations (visual or auditory), dissociations, disorientation, agitation
- Inappropriate laughter or exhilaration
- Misuse of IMP
- Mood changes
- Overdose
- Thoughts of suicide, attempted suicide, or suicide

An AE that is consistent with the above categories will be known as a 'triggering AE of interest' for the purposes of this trial.

# 9.2.18.1.2 Supplemental Adverse Event Form (Abuse Liability)

This form consists of 12 questions regarding the AE and the use of IMP. It is completed as part of an interview with the patient when a triggering AE of interest is reported. It is important that this is completed by a trained investigator or trial coordinator with the patient present. The answers on the Supplemental Adverse Event Form will then be entered into the patient's eCRF for the trial. If the Supplemental Adverse Event Form cannot be completed at the time the triggering AE of interest is reported, then the trial site should contact the patient to obtain the required answers as soon as possible. The time and date of collection must be recorded in the patient's notes and on the eCRF.

#### SPONSOR: GW PHARMA LIMITED

# 9.2.18.2 Monitoring Drug Accountability Discrepancies (Abuse Liability)

Any time after randomization until final collection of trial data, drug accountability discrepancies are monitored as follows:

- At routine drug accountability collection times (i.e., Visits 3, 4, 5, and 6)
  - The site personnel will collect the IMP clinical supplies and make sure the usage is in line with the expectations reported within the electronic diary
- At any time that the trial site is informed by the patient about any overuse of IMP, suspected misuse, abuse, or diversion

# 9.2.18.2.1 List of Triggering Drug Accountability Discrepancies (Abuse Liability)

If there are any discrepancies in drug accountability as outlined by the criteria below, known as 'triggering drug accountability discrepancies', then the trained investigator or trial coordinator will complete a Supplemental Drug Accountability Form (see Section 9.2.18.2.2) and a Site Classification Form (investigator only; see Section 9.2.18.3) following further discussion of the event(s) with the patient. The triggering drug accountability discrepancies are as follows:

- Compliance issues where 1 or more vials are used compared to the expected use, according to the electronic diary entries and drug accountability calculations in eCRF
- Greater than the target daily dose as recorded in the electronic diary
- Missing vial(s)
- Returned IMP supply with evidence of tampering

# 9.2.18.2.2 Supplemental Drug Accountability Form (Abuse Liability)

This form consists of 10 questions regarding various aspects of drug accountability and patient usage. It is completed as part of an interview with the patient when a triggering drug accountability discrepancy is identified. It is important that this is completed by a trained investigator or trial coordinator with the patient present. The answers on the Supplemental Drug Accountability Form will then be entered into the patient's eCRF for the trial. The accountability reporting procedures will still occur (see Section 5.3.4). If the Supplemental Drug Accountability Form cannot be completed at the time the triggering drug accountability discrepancy is identified, then the trial site should contact the patient by telephone to obtain the required answers as soon as possible. (Note: IMP refers to nabiximols or placebo, not other concomitant medications).

#### SPONSOR: GW PHARMA LIMITED

# 9.2.18.3 Site Classification Form (Abuse Liability)

The investigator should review the applicable Supplemental Adverse Event Form or Supplemental Drug Accountability Form, and should then complete the Site Classification Form. For each Supplemental Adverse Event Form or Supplemental Drug Accountability Form completed, there should be an associated Site Classification Form.

The Site Classification Form requires the investigator to assign the finding to an appropriate classification and then to also assign the possible relationship to the IMP. The investigator is also required to indicate the level of certainty of the classification. The answers from the Site Classification Form will then be entered into the patient's eCRF for the trial.

# 9.2.18.4 Adjudication Committee: Assessment of Abuse Potential of Nabiximols

A formal adjudication committee will be appointed and assigned to this initiative to classify triggered cases. The adjudication committee will meet on a periodic basis to review and assess all of the information collected on triggered cases. Only data from patients who have completed the trial will be assessed.

A detailed charter will be agreed, which will describe the roles, responsibilities, and duties of the members of adjudication committee. The adjudication committee will review all of the information collected in the process and in the assessment of the abuse potential of nabiximols, such as:

- Additional information from trial site(s) as requested by the adjudication committee
- All triggering AE information
- All triggering drug accountability discrepancies
- Site Classification Form
- MUS
- Supplemental Adverse Event Form (if applicable)
- Supplemental Drug Accountability Form (if applicable)

The adjudication committee will assess all of the information. It will form an opinion on the classification of each event and will write a trial-related report, detailing the conclusions and recommendations.

The overall process is summarized in Figure 9.2.18-1.

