8.4 Adjudication Committee

A formal adjudication committee, blinded to treatment arm will classify triggered cases related to abuse potential, based on adverse events and drug accountability.

A separate adjudication charter will define and describe the procedure for the handling, reporting, and classification of these events.

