9.4.2 Analysis Sets

Analysis Set	Abbreviation (if applicable)	Definition
Screening Analysis Set		All patients who signed the informed consent and have performed Visit 1 (Screening).
Safety Analysis Set	SAF	All patients, from the Screening Analysis Set, who received at least 1 dose of IMP in the trial. Only patients for whom it has been confirmed that they did not take IMP will be excluded from the Safety Analysis Set, for example where this is reported as a protocol deviation
Full Analysis Set	FAS	All patients from the SAF who signed the informed consent and are randomized by IRT.
Pharmacokinetic Analysis Set	PK Analysis Set	All patients who have received at least 1 dose of nabiximols and provided sufficient bioanalytical data to calculate reliable (based on the judgement of the pharmacokineticist) estimates of the PK parameters of THC, CBD, and their metabolites. For the purposes of biostatistics and programming team this will be patients who have taken at least one dose of nabiximols and have at least one PK parameter concentration and will be determined post unblinding; The final PK population being defined by the pharmacokineticist.

Table 9.4-1 Analysis Set Definitions and Abbreviations

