12.8.6 Monitoring of Drug Abuse Liability

Using the Potential Misuse, abuse and diversion drug event reporting System (MADDERS) "Site classification form" as reported in EDC, a summary of patients triggered for potential abuse-related adverse events will be provided by Visit (Visit 3 (titration phase), Visit 4, Visit 5 and Visit 6), for the maintenance phase (Visit 4, Visit 5 and Visit 6) and for the 12-Week on-treatment period using the SAF during the 12-week on-treatment period.

The summary will present

- The number of adjudicated events
- The number and percentage of patients with at least one adjudicated event
- The number of adjudicated events related to IMP
- The number and percentage of patients with at least one trigger event related to IMP
- The number and percentage of patients by category of type of event:
 - Tampering
 - Withdrawal
 - Addiction related indication
 - Diversion
 - Overdose

As reported by site personnel.

This summary will be repeated based on the final adjudication assessment.

Furthermore, the number and percentage of patients with at least

- one supplemental drug accountability form (MADDERS) completed
- one supplemental adverse event form (MADDERS) completed

will also be summarized by treatment arm.

The MADDERS medication use survey is a 6-item questionnaire, the 1st item includes 3 additional subitems and the 4th item has 2 parts. Each item/sub-item is being scored as "Never", "Seldom", "Sometimes" and "Often". The questionnaire is taken at end of treatment visit. Each item will be summarized by treatment arm.

Patient wise listings of the events with respect to site/investigator classification and adjudication classification will be presented.

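### As written, Protocol 9.2.18.4 leaves triggered abuse-potential cases in patients who leave the trial early without blinded committee classification

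*Protocol*

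**What the plan says.** Protocol 9.2.18.4 sets up a committee to classify triggered cases, that is, cases raised by an adverse event of interest or a drug accountability discrepancy. On scope it says: "The adjudication committee will meet on a periodic basis to review and assess all of the information collected on triggered cases". The next sentence restricts this: "Only data from patients who have completed the trial will be assessed". The section then lists the committee's inputs and closes with its output: "It will form an opinion on the classification of each event and will write a trial-related report, detailing the conclusions and recommendations".

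SAP 8.4 describes a committee "blinded to treatment arm will classify triggered cases related to abuse potential, based on adverse events and drug accountability". It states no completer condition and refers the procedure to a separate charter. SAP 6.2 declares no change from the protocol.

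SAP 12.8.6 plans a summary of triggered patients from the site classification, "for the 12-Week on-treatment period using the SAF during the 12-week on-treatment period", and adds: "This summary will be repeated based on the final adjudication assessment". It also plans listings: "Patient wise listings of the events with respect to site/investigator classification and adjudication classification will be presented". The addendum (section 7.0, Table 7-1) keeps 12.8.6 but drops the summary of triggered events.

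**The concern.** The committee is the formal layer above the investigator's own classification. According to SAP 8.4 it works blinded to treatment arm, and its report carries the conclusions on abuse potential. If only completers are assessed, a post-randomization outcome decides which triggered cases get that review.

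That outcome can follow from the event itself. Protocol section 10 foresees patients withdrawing because of an adverse event. The triggering categories in 9.2.18.1.1 include hallucinations, intoxication, euphoria, overdose and suicidality. A patient who leaves the trial because of such an event would, on the text, fall outside the committee's assessment.

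**Working it through.** No figure in the plan bears on this point, so the check is a comparison of passages.

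**1. What completing the trial means.**
- Protocol 4.1 gives completers about 127 days in total, which is the 28 baseline days plus follow-up to Day 99 (28 + 99 = 127).
- Protocol 9.2.13 has the IRT record either completion or premature termination.
- Protocol 13.3 builds the per protocol set on patients who completed the trial.
- SAP 12.1 tabulates completion separately from early discontinuation of the study.

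None of these places counts a withdrawn patient as having completed. In the documents' own usage, the restriction excludes early leavers.

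**2. Who is an early leaver.** Protocol section 10 requires withdrawal from the trial for an administrative decision, withdrawn consent or loss to follow-up. Patients who stop study drug for other reasons should remain in the trial. Those reasons include adverse events, suicidality and evidence of abuse or diversion. Such patients can still complete and be adjudicated. The gap therefore concerns patients who leave the trial, not everyone who stops treatment.

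**3. The restriction against its own section.** The committee is to assess all information on triggered cases and form an opinion on each event. It cannot do this for each event if it sees only completers' data, unless the restriction concerns timing alone.

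**4. The restriction against the SAP.** SAP 8.4 has no completer condition and SAP 6.2 declares no change, so the SAP does not settle which rule applies. In the 12.8.6 listings, a triggered early leaver would have a site classification and no adjudication classification. No instruction says how to show or explain that.

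**5. Whether the data give a reason for the restriction.** The listed inputs are:
- extra site information, on committee request;
- triggering adverse event information, collected when the patient reports the event (9.2.18.1.1);
- accountability discrepancies, monitored from randomization until final data collection (9.2.18.2);
- the Site Classification Form, one per supplemental form (9.2.18.3);
- the Medication Use Survey (MUS), at the End of Treatment or Withdrawal Visit (9.2.18);
- the two supplemental forms, completed when the trigger is reported or identified (9.2.18.1.2, 9.2.18.2.2).

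None is made conditional on completing the trial. This shows that the material can exist for early leavers; it does not measure impact. The MUS needs a caveat. Protocol 13.6.2 says withdrawing patients are required to do the Visit 6 procedures. The synopsis and 4.1 are softer: the withdrawal visit is requested at the investigator's discretion and where possible, with exceptions for withdrawn consent and loss to follow-up. Some packets will therefore lack the MUS.

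**6. Size.** The documents give no withdrawal rate and no trigger rate. The share of triggered cases affected cannot be computed, and any percentage would be assumption alone.

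**The case against.** The strongest defence is that the sentence is a timing rule. It directly follows the statement that the committee meets periodically, and one input, the MUS, is collected only when the patient finishes or withdraws. Waiting until a patient's participation has ended would fit this, and would also fit the instruction to consider all information on each event. The reading is plausible and stands as a possibility. But the sentence says completed, not finished or withdrawn, and nothing nearby widens it. The charter or Figure 9.2.18-1 may settle the matter; neither was available, and that limits the point.

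A reader might also infer more than the documents support:
- *That SAP 12.8.6 promises adjudication of every trigger in the Safety Analysis Set.* That set is defined by dosing ("All patients, from the Screening Analysis Set, who received at least 1 dose of IMP in the trial"), but naming an analysis population does not promise that every case in it is adjudicated. The summary that used the set is dropped by the addendum, and the surviving listings sentence names no population.
- *That patients stopped for abuse or diversion are excluded.* Section 10 says they should remain in the trial.
- *That 9.2.15.4 requires every triggered case to be adjudicated.* It says only that patients without a trigger are not adjudicated.
- *That the early termination turned patients then on study into non-completers.* The documents do not say how those patients were handled.

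**Conclusion.** The point holds as a defect of wording with a real, bounded consequence. Followed as written, Protocol 9.2.18.4 leaves triggered cases in early leavers without blinded committee classification and outside the committee's report, against the remit in the same section. This rests on the documents' own use of completion and on the absence of any text making the sentence a timing rule. A charter provision covering withdrawn patients would narrow the point to reconciling two documents.

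The effect is limited to patients who leave the trial. Their Site Classification Forms and TEAE reporting remain, and the primary efficacy analysis is untouched. After the addendum, only the committee report and the 12.8.6 listings are affected. The number of cases is unknown. This is a cheap improvement, not a threat to the trial's main conclusions.

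**What to change.** Replace the sentence with: *All triggered cases will be adjudicated, whether the patient completed or withdrew from the trial, once that patient's available data are final.* This serves either reading: it keeps the waiting rule if timing was the intent, and it removes the exclusion. Align the charter. In the SAP 12.8.6 listings, mark any triggered case that was not adjudicated and give the reason.

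The cost is one sentence, a matching charter edit, a marker with reason in the listings, and a few more case packets for an existing committee. A protocol change would also go through the amendment process in Protocol 16.1. The downside is that some packets will be incomplete, for example without an MUS in patients lost to follow-up, and may end without a firm classification.
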